18.0 Sharing of Results

18.1

All measures (surveys, games, microbiome, blood spot, and interview) are for research purposes only and individual results may not be meaningful. Participants will not be told of individual results for any measures. No study data will be shared with participants' health records.

18.2

Study results may be shared with the public via manuscripts and/or open source databases. The Center for Healthy Minds website and/or other social media platforms will share information on study results and/or publications.

19.0 Data and Specimen Banking

PROTOCOL TITLE: Behavior, Biology, and Well-Being (BeWell) Study

19.1

Banking of data and specimens will not be optional. Coded data and specimens from participants may be banked for future use to address research questions not included in this protocol. The code linking to identifying information will be kept on a password-protected server and ICTR's instance of REDCap with access limited to specific study personnel.

19.2

The code linking data and specimens to identifying information will be accessed in ICTR's instance of REDCap and on a password-protected server with access limited to specific study personnel.

19.3

We are not placing any limits on the intended future use of data, and any future research utilizing these data will be submitted as a separate application to the IRB prior to their use, if required by IRB policies and/or guidance. Genetic analyses are limited to the following:

- Whole genome analysis of the bacterial genome.
- mRNA analyses of dried blood spot to evaluate gene expression. Analyses will focus on transcripts from ~200 genes known to be involved in the regulation of inflammation and summary measures reflecting the activity of transcriptional networks that coordinate inflammation (NF- κ B, AP-1).

Data may be requested by other researchers at UW-Madison as well as by researchers outside of UW-Madison to the study PI and/or Co-Investigators.

19.4

Participants may withdraw their samples and data from banking for future research. If there are any residual amounts from their dried blood spot and stool samples, they will be destroyed. Any data that has been shared in an open source format or as part of a journal database will be de-identified and thus cannot and will not be withdrawn.

20.0 Study Analysis

20.1

HMP will show greater improvements in (a) depression, (b) psychological distress, (c) well-being, (d) and performance on the pattern separation task vs. both the active control (HMP psychoeducation) and usual care conditions.

20.2

We plan to enroll 1500 participants in this study, assigning two fifths to HMP, two fifths to the active control, and one fifth to a usual care. Anticipating 20% dropout, this sample will provide 80% power to detect small differences between HMP and the active control ($d = 0.20$) and 80% power to detect small-to-moderate differences between HMP and the usual care ($d = 0.28$).

PROTOCOL TITLE: Behavior, Biology, and Well-Being (BeWell) Study

We plan to recruit approximately 250 healthy controls at baseline. This will allow statistical power to detect small between-group differences on baseline measures.

20.3

Participants will be randomized into 3 different groups: two-fifths to intervention, two-fifths to active control and one-fifth to waitlist control. All study procedures will be the same across all groups except the use or non-use of HMP.

Healthy control participants will not be randomized.

20.4

Group differences for the intervention will utilize linear mixed effects models to account for non-independence and to maximize use of data with missing observations.

20.5

Given the low risk of the intervention, no interim efficacy or safety analyses are planned.

20.6

Linear mixed effects analyses account for missing data in a robust manner relative to, e.g., ANOVA. If differential attrition is observed (e.g., between HMP and usual care), we may conduct sensitivity analyses to evaluate the potential impact of data missing not at random.

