4.0 Number of Participants

4.1

This study will enroll 1,500 participants at UW-Madison. There will also be a pilot of up to 15 participants. We will recruit approximately 250 healthy control participants who will complete baseline measures only.

4.2

The expectation is that we will have 20-50% attrition resulting in roughly 750-1200 participants completing the study.

4.3

Participants will be considered enrolled after randomization. Participants who leave the study early will not be replaced. Healthy control participants will only complete baseline measures.

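### The two detectable effects in section 20.2 cannot both be 80%-power values under one alpha; no alpha is stated, and power is given only at the favourable end of the expected attrition range

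*Combined protocol and SAP*

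**What the plan says.** Section 20.2 sets the design: "We plan to enroll 1500 participants in this study, assigning two fifths to HMP, two fifths to the active control, and one fifth to a" (the last arm being usual care). Section 20.3 repeats the 2:2:1 split ("two-fifths to intervention, two-fifths to active control and one-fifth to waitlist control"). The power claim in 20.2 has two parts:

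- HMP vs active control: "Anticipating 20% dropout, this sample will provide 80% power to detect small differences between HMP and the active control ($d = 0.20").
- HMP vs usual care: "80% power to detect small-to-moderate differences between HMP and the usual care ($d = 0.28").

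One dropout rate and one power level serve both comparisons. No significance level, sidedness, multiplicity rule, test or variance assumption is given in 20.2 or elsewhere in the document.

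On attrition, section 4.2 says: "The expectation is that we will have 20-50% attrition resulting in roughly 750-1200 participants completing the study". On analysis, section 20.4 says: "Group differences for the intervention will utilize linear mixed effects models to account for non-independence and to maximize use of data with missing observations".

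**The concern.** When two comparisons share an arm, an alpha, a power and a dropout rate, the ratio of their detectable effects is fixed by the arm sizes alone. The pair in 20.2 does not have that ratio, so at least one figure was obtained in a way the section does not describe. Without an alpha, a reader cannot tell which.

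The second issue matters more for interpretation. Power is quoted only at 20% dropout, the best case in section 4.2. The active-control comparison separates the guided practices from the lessons (section 11.1) and has the smaller target effect. If attrition lands in the upper part of the expected range and that comparison is null, readers will credit the trial with 80% power for d = 0.20 that it may not have had.

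**Working it through.** **Inputs.** N = 1,500 at 2:2:1 gives 600/600/300 (20.2, 20.3). 20% dropout, assumed equal across arms, leaves 480/480/240 (20.2). 50% attrition leaves 300/300/150 (upper end of 4.2). Power is 80% and d is in SD units (20.2). Alpha is not stated, so two-sided 0.05 and 0.025 are assumed, with one-sided 0.05 as a further variant.

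**Formula.** Detectable d = (z for alpha + z for power) × sqrt(1/n1 + 1/n2). The results below use the noncentral t, which at 20% dropout agrees with this formula to within 0.001.

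**Step 1: try to reproduce the stated figures at 20% dropout.**

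| Two-sided alpha | 80%-power d vs active control (480 vs 480) | 80%-power d vs usual care (480 vs 240) | Power at d = 0.20 / 0.28 |
|---|---|---|---|
| 0.05 | 0.181 | 0.222 | 87.2% / 94.3% |
| 0.025 | 0.199 | 0.244 | 80.3% / 90.2% |

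The active-control figure of 0.20 reproduces at 0.025. The usual-care figure of 0.28 reproduces at neither alpha.

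**Step 2: the ratio test, free of alpha.** With common alpha, power and variance factor, those terms cancel:

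sqrt(1/480 + 1/240) / sqrt(1/480 + 1/480) = sqrt(1.5) = 1.22.

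The stated ratio is 0.28/0.20 = 1.40. Rounding allows 0.275/0.205 = 1.34 to 0.285/0.195 = 1.46, which excludes 1.22.

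**Step 3: the alpha each figure implies at exactly 80% power.**

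- d = 0.20, 480 vs 480: 0.0243 (0.0198 to 0.0296 after rounding of d).
- d = 0.28, 480 vs 240: 0.0071 (0.0059 to 0.0086).

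The ranges do not overlap. At alpha 0.0071, power for d = 0.20 at 480 vs 480 would be only 66%.

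**Step 4: possible sources of 0.28.** Two calculations give about the stated value, and the document supports neither: 240 vs 240 at two-sided 0.025 gives 0.282 (the larger HMP arm ignored), and 300 vs 150 at two-sided 0.05 gives 0.281 (50% attrition rather than 20%).

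**Step 5: the upper end of the section 4.2 range, completers only (300/300/150).**

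| Two-sided alpha | 80%-power d vs active control | 80%-power d vs usual care | Power at d = 0.20 / 0.28 |
|---|---|---|---|
| 0.05 | 0.229 | 0.281 | 68.6% / 79.8% |
| 0.025 | 0.252 | 0.309 | 58.0% / 70.9% |

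At one-sided 0.05, power for d = 0.20 is 79%.

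Attrition beyond which 80% power for d = 0.20 vs active control is lost: 34.4% at two-sided 0.05, 20.6% at two-sided 0.025, 48.4% at one-sided 0.05. All three lie inside 20-50%.

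**Step 6: allowance for baseline adjustment.** Multiplying the variance by 1 − r², with assumed r = 0.3 / 0.5 / 0.6, power for d = 0.20 at 300 vs 300 becomes 73 / 81 / 86% at two-sided 0.05 and 63 / 72 / 79% at 0.025.

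**The case against.** Four points can be made for the plan.

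1. *The claim may mean at least 80% power.* On that reading both statements are true together at any two-sided alpha of about 0.024 or more, including 0.05. This stands as to direction: at 20% dropout nothing is overstated. It does not rescue the pair as written, because quoting two different effects at the same 80% presents them as detectable effects, and 0.28 is not one for 480 vs 240 at either usual alpha.

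2. *The planned analysis is a mixed model, not a completers' comparison.* PHQ-8 is collected at six assessments (section 13.3), and some people who do not finish the study will contribute earlier data. So the completers-only figures are probably pessimistic. With r = 0.5 at two-sided 0.05, power at 50% attrition returns to 81%. At 0.025, the alpha at which the active-control figure reproduces, it stays below 80% for every correlation tried. The plan gives no correlation, so the gain cannot be credited. A gain common to both comparisons also cancels in the ratio and cannot explain the mismatch.

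3. *The usual-care claim is largely robust to attrition.* This is correct. At two-sided 0.05, power for d = 0.28 is still 79.8% at 50% attrition; at 0.025 it holds to about 39%. The attrition problem is mainly one for the active-control comparison.

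4. *Dropout might differ by arm*, a possibility section 20.6 raises. With 480 in each app arm, a ratio of 1.40 would need about 164 usual-care completers, or 45% dropout in that arm. The rounding limit of 1.34 would need about 185, or 38%. Section 20.2 states a single 20% rate.

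Finally, 20% lies within 20-50%, so the two sections do not contradict each other. The gap is that only the favourable end is carried into the power statement.

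**Conclusion.** The concern holds. As written, d = 0.20 and d = 0.28 cannot both be 80%-power effects for 480/480/240 under a common alpha: the ratio must be 1.22 and is 1.40. If alpha was two-sided 0.025, the usual-care figure should be 0.24; if 0.05, the pair should be 0.18 and 0.22. This rests on equal dropout across arms and a variance factor common to both comparisons. It does not depend on the alpha.

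The mismatch is conservative at 20% dropout and does not show the trial to be underpowered there. The consequential gap is the missing alpha together with the single attrition scenario. On completers, power for d = 0.20 against active control falls below 80% beyond about 34% attrition (two-sided 0.05) or 21% (0.025), and reaches 69% or 58% at 50%. Those figures assume no gain from the mixed model, so they are cautious. This should be fixed; it does not call the design into question.

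**What to change.** Rewrite the power paragraph in section 20.2 so that it:

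- states the alpha, the sidedness, any adjustment for the two comparisons, and the formula or software used, including any baseline correlation assumed for the mixed model;
- recomputes the usual-care effect with the actual 2:1 arms;
- gives both detectable effects across the attrition range of section 4.2.

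Suggested wording: *At [alpha, sidedness, adjustment], with attrition of 20% to 50% (480/480/240 to 300/300/150 completers), the trial has 80% power to detect d = [a to b] for HMP against active control and d = [c to d] against usual care.*

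Completer-based values to insert: 0.18 to 0.23 and 0.22 to 0.28 at two-sided 0.05; 0.20 to 0.25 and 0.24 to 0.31 at two-sided 0.025. If the authors rely on the mixed model for better figures, they should state the correlation and show those figures alongside.

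The cost is one reworded paragraph once the authors confirm the alpha they used, and a less favourable worst case on record. Enrolment and allocation are unchanged.

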13.0 Procedures Involved

13.1 Study Design

After potential participants are informed of their eligibility, they will be invited to complete the following steps:

1. Consent Process. Individuals will read a consent script in REDCap and are given the opportunity to reach out to study staff if they have any questions or concerns about study procedures before clicking on the box indicating interest in participating in the study.
2. Pre-Intervention Assessment (Timepoint 1). A REDCap link for these surveys and games (behavioral task and video task) will be sent after consent is completed. It will take approximately 60-90 minutes to complete these measures. Potential participants will be given two weeks to complete this assessment. In order to increase study retention, only those who complete this assessment will be invited to subsequent parts of the study. A microbiome and blood spot collection kit will be mailed to participants to be completed before randomization occurs. The kit needs to be returned within one month of completing the surveys and games to continue with the randomization step.
3. Interview. The participant will undergo an interview conducted by research staff who are trained in interviewing techniques and supervised by qualified study personnel with mental health expertise. The interview will consist of the depression and related modules of the Structured Clinical Interview for DSM-5 Research Version (SCID-5-RV). The interview will be done via phone or video and will take approximately 60 minutes to complete. Participants may be sent an email to confirm their current phone number, interview time, and/or other details to assist with interview scheduling.
4. Randomization. Participants will be assigned to one of three groups: approximately two-fifths to the HMP intervention group, approximately two-fifths to the active control group, and approximately one-fifth to the usual care group. Randomization will be done in REDCap (either immediately after the interview or within a few days if consultation with a study PI or Co-I is needed; the microbiome and blood spot kit need to be returned before randomization). A REDCap alert will inform participants of group status immediately after randomization along with instructions for downloading HMP for those in the intervention and active control groups.

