5. Weeks 1 to 3 Assessments (Timepoints 2, 3, 4). Participants will complete a small subset of the surveys in REDCap as well as the video task at the end of weeks 1, 2, and 3. It will take

PROTOCOL TITLE: Behavior, Biology, and Well-Being (BeWell) Study

approximately 30 minutes to complete these measures. Participants will be given one week to complete each weekly assessment.

6. Week 4/Post-Intervention Assessment (Timepoint 5). Participants will complete the same surveys and games (behavioral task and video task) in REDCap as was done for the pre-intervention assessment; the invite for these measures will be sent at the end of week 4. It will take approximately 60-90 minutes to complete these measures. Participants will be given 2 weeks to complete this assessment. Participants in the intervention or active control groups will have the option to continue using the HMP after this timepoint. We will continue to monitor app data throughout the study to learn more about its long-term impact on well-being.
7. 3-Month Follow-Up Assessment (Timepoint 6). Participants will complete the same surveys and games (behavioral task and video task) in REDCap as was done for the pre-intervention and post-intervention assessments; the invite for these measures will be sent 90 days after the date of the post-intervention invite. It will take approximately 60-90 minutes to complete these measures. Participants will be given 2 weeks to complete this assessment. Another microbiome kit and blood spot collection kit will be mailed to participants to collect samples; they will have 1 month to collect.

Healthy control participants will complete only #1 to #3.

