◆ Pattern separation. Meditation training has the capacity to normalize the overgeneralized inflexible cognition endemic to depression, which is hypothesized to relate to alterations in the hippocampal-dependent process of pattern separation. We will use a pattern separation task sensitive to meditation training to be completed at the pre-intervention, post-intervention, and 3-month follow-up assessments via a REDCap link.

◆ Video recording measures. Participants will be asked to provide video recordings of their face and voice while responding to prompts at all time points (T1 to T6). These prompts may involve responding to a recorded prompt (e.g., cartoon image), watching brief videos of positive or negative valence (e.g., baby giggling, someone telling a sad story), or sharing information about their day or week (e.g., “tell us something positive that happened

PROTOCOL TITLE: Behavior, Biology, and Well-Being (BeWell) Study

this week"). These recordings provide the opportunity to explore indicators of self-referent, inflexible, & over-generalized thinking within natural language that can be compared to behavioral measures indicated above. Data from recordings will be used to explore novel measures that once developed can be acquired without active input from the user on mobile devices and extracted from several data streams including facial features, vocal indicators and content analysis of text. Video data will be analyzed using various machine learning methods (e.g., Google's Gemma). Data will be analyzed using models run locally which will eliminate confidentiality risks. Platforms used for video analysis will be vetted by the HIPAA security office prior to use.

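### Pattern separation and the scalar blood and stool outcomes have no weekly scores, so an outcome-only mixed model does not use the weeks 1-3 symptom data and can be biased if symptom-related dropout differs by arm

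*Combined protocol and SAP*

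**What the plan says.** **Method.** Section 20.4: "Group differences for the intervention will utilize linear mixed effects models to account for non-independence and to maximize use of data with missing observations". Section 20.6 adds that "Linear mixed effects analyses account for missing data in a robust manner relative to, e.g., ANOVA" and that, if attrition differs between groups, "we may conduct sensitivity analyses to evaluate the potential impact of data missing not at random". No auxiliary variables, imputation, weighting or joint model are named.

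**Timing of the outcomes.**
- Pattern separation (secondary endpoint in 3.3, claim 20.1(d)) is "to be completed at the pre-intervention, post-intervention, and 3-month follow-up assessments via a REDCap link", that is, at T1, T5 and T6.
- Blood and stool: "A microbiome and blood spot collection kit will be mailed to participants to be completed before randomization occurs", and then at the 3-month follow-up, "Another microbiome kit and blood spot collection kit will be mailed to participants to collect samples". There is no T5 sample. Biological change is an aim (3.1) and a hypothesis (3.2), but is not a listed endpoint in 3.3.
- At weeks 1-3 (13.1, step 5), participants complete "a small subset of the surveys in REDCap as well as the video task at the end of weeks 1, 2, and 3". The measures table in 13.3 marks PHQ-8 and GAD-7 at the weekly timepoints without the restriction to app groups that some other scales carry.

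**Attrition.** Section 4.2 expects that "we will have 20-50% attrition"; section 20.2 plans on 20%.

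**The concern.** A likelihood-based mixed model is valid under missing at random given the data in that model. For PHQ-8, the weekly scores are among those data. For pattern separation, a participant lost before T5 contributes only the T1 value, so the model assumes that, given this value and arm, leaving is unrelated to the missing result. For blood and stool the same applies to anyone without a T6 sample.

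Meanwhile the trial records symptom course during the four weeks in all three arms. If that course influences who stays, does so differently by arm, and is related to the outcome, the stayers are no longer comparable. Equal dropout rates do not protect against this, and the sensitivity analysis in 20.6 is both optional and triggered by unequal attrition. At stake are claim 20.1(d) and the biological hypotheses.

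**Working it through.** **1. The plan's own figures.** The plan gives no figure for missing-data bias. Its only computed figures are the powers in 20.2: 80% at d = 0.20 and 80% at d = 0.28, after 20% dropout from 1,500 randomized 2:2:1. With alpha assumed 0.05 two-sided (none is stated):
- 480 vs 480: SE = √(2/480) = 0.0645; 0.20/0.0645 = 3.10; power = Φ(3.10 − 1.96) = 87.3%.
- 480 vs 240: SE = √(1/480 + 1/240) = 0.0791; 0.28/0.0791 = 3.54; power = Φ(3.54 − 1.96) = 94.3%.

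The stated powers do not reproduce. This point does not depend on them; they only supply the effect sizes used for scale.

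**2. Inputs for the bias.** From the documents: 600 HMP, 300 usual care, dropout 20-50%. Assumed, because the documents are silent:
- true effect 0;
- T1-T5 correlation 0.6;
- W, the standardized weeks 1-3 change in PHQ-8, independent of Y1;
- slope b of the outcome on W, 0.1 to 0.3 in absolute value;
- dropout odds ratio per SD of W, 1.5 to 2.0 in HMP and 1.0 in usual care;
- the same overall dropout rate in both arms.

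**3. Formula.** Let Y5 = 0.6·Y1 + b·W + e, with total variance 1. Regression on Y1 among those observed stands in for the outcome-only mixed model. Since W is independent of Y1 and selection acts only in HMP:

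absolute bias = |b| × |E(W | stays, HMP)|

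The expectation is the integral of w·(1 − p(w))·φ(w), divided by (1 − dropout rate), where p(w) is the logistic dropout probability and its intercept is set to give the overall rate. The residual SD given Y1 is √(1 − 0.36) = 0.8, so SE = 0.8 × √(1/n₁ + 1/n₀).

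| Dropout | Shift in mean W among HMP stayers, OR 1.5 / 2.0 | Absolute bias, \|b\| 0.1-0.3 (SD) | SE | Type I error |
|---|---|---|---|---|
| 20% | 0.079 / 0.129 | 0.008-0.039 | 0.063 | 5-9% |
| 35% | 0.137 / 0.220 | 0.014-0.066 | 0.070 | 5-16% |
| 50% | 0.195 / 0.313 | 0.020-0.094 | 0.080 | 6-22% |

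Worked case (35%, OR 2.0, b = 0.3): bias = 0.3 × 0.220 = 0.066. SE = 0.8 × √(1/390 + 1/195) = 0.070. The ratio is 0.94, so two-sided error = P(Z > 1.02) + P(Z < −2.90) ≈ 15.6%.

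Simulation of the same model (600 trials per scenario) gave bias of 0.01-0.04, 0.02-0.07 and 0.02-0.10 SD, and type I error of 4-10%, 6-16% and 5-22%. Monte Carlo error on the type I error is about 1 point.

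**4. A second model.** This was a large-sample simulation with 400,000 per arm, baseline correlation 0.5, dropout log-odds 0.7 per SD of week-3 symptoms and residual symptom-outcome correlation 0.1 to 0.5.
- Dropout driven by symptoms in HMP only, equal rates: 0.007-0.107 SD over 20-50% dropout.
- Same slope, but 20% vs 50% dropout: 0.014-0.064 SD.
- Same slope and equal rates: about 0.
- No symptom-outcome correlation, or dropout unrelated to symptoms: about 0.
- Adding baseline symptoms alone did not remove the bias; adding week-3 symptoms did, to within 0.007 SD.

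**5. What the fix recovers.** If every dropout has a weekly score, by-arm imputation leaves at most about 0.003 SD, with type I error of 4-7% and nearly the same SE. If half of the dropouts lack the weekly score (b = 0.3, OR 2.0), the remaining bias is 0.017 of 0.038 SD at 20% dropout, 0.026 of 0.066 at 35% and 0.030 of 0.093 at 50%. That is roughly a third to a half.

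**The case against.** The strongest reply is that the bias needs three things together: symptom-related dropout, a residual symptom-outcome link, and a difference between arms. The documents give no data on any of them. This stands. Section 13.3 does tie pattern separation to the cognition seen in depression, so a link is plausible, but its size is not given. At the 20% dropout used for planning, the bias is small even under the strongest of the step 3 assumptions.

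The reach is also limited. A reader might infer that the trial's whole handling of missing data is unsound. The documents do not support that: PHQ-8, GAD-7, sleep disturbance, flourishing and the video task are all collected weekly, so of the endpoints in 3.3 only pattern separation is affected. A reader might also carry the figures over to the active-control contrast or to the biomarkers. The step 3 calculation covers neither. HMP and active control both use versions of the same app for four weeks, so similar dropout mechanisms are at least as plausible there. The biomarkers have no T5 value.

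Finally, sections 20.4 and 20.6 do not list model terms, so non-use of the weekly scores is inferred from silence. Dropout driven by a score outside the model is also, relative to that model, missing not at random, which is what the 20.6 sensitivity clause addresses. But that clause is discretionary and depends on differential attrition, so it need not be applied in the equal-rate case shown here.

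**Conclusion.** The point holds as a gap in prespecification with a cheap remedy, not as a demonstrated bias. For HMP versus usual care on a T5 outcome, the assumed inputs give about 0.01-0.04 SD at 20% dropout and up to about 0.09-0.10 SD at 50%. Against the d = 0.28 in 20.2, the upper ends are 0.039/0.28 = 14% and 0.094/0.28 = 34% of the target effect. With the same mechanism and dropout rate in both arms, the bias is near zero.

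The structural argument extends to scalar blood and stool summaries at T6, but no size has been worked out for them. The primary endpoint is not affected in this way. It would go too far to say that the plan's contrasts are biased, or that symptoms are known to drive dropout: the documents contain no evidence on why participants leave.

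**What to change.** Add to section 20.6, before arm-level results are seen:

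- For pattern separation (T5 and T6) and for scalar biomarker summaries (T6 only), impute missing values by multiple imputation separately by arm and then fit the planned mixed model. A joint mixed model of the outcome with the repeated symptom scores is an alternative.
- Use the baseline outcome and all available PHQ-8 and GAD-7 scores as auxiliary variables. Do not enter the weekly scores as covariates in the outcome model: they are measured after randomization and would adjust away part of the treatment effect.
- Impute partly missing weekly scores in the same model.
- Report the outcome-only mixed model alongside, and do not make this analysis conditional on differential attrition.

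The cost is SAP wording, an imputation model to prespecify and some programming; no new data are needed. The bias is only partly removed for participants who leave before giving weekly scores. Multivariate microbiome outcomes such as beta diversity and clusters lie outside this fix.
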